### 9.2 Analysis Populations Definitions

The Full Analysis Set (FAS) will include all subjects who are randomised to GT005 or untreated control. The Safety Analysis Set (SAF) will include all subjects who are randomised to the GT005 or control group and provide at least one post baseline observation.

### 9.3 Significance Testing and Estimations

Type 1 error (alpha) is set at 0.05 one-sided and estimates of outcome parameters will be accompanied by 90% confidence intervals to be consistent with the Type 1 error level. No multiplicity adjustment will be applied since this is an exploratory study.

### 9.4 Statistical/Analytical Methods

#### 9.4.1 Demographics and Baseline Characteristics

Demographic and baseline characteristics including age, race, ethnicity, sex, as well as baseline GA lesion size, will be summarised with descriptive statistics or counts and percentages of subjects as appropriate by treatment and in total for each defined analysis population.

#### 9.4.2 Efficacy Assessments

The primary endpoint, change from baseline to Week 48 in GA area, will be compared between treatments via least squares means from analysis of covariance (ANCOVA). The primary estimand will focus on the effect of different doses of GT005 on GA change on FAF at Week 48 and account potential unfavourable effects of GT005. The primary estimand includes the following components:

- Population: subjects with GA secondary to AMD
- Variable: Change from baseline in GA lesion size on FAF at Week 48

- Treatment: the randomised treatment of the investigational therapy GT005
- Intercurrent events: defined in [Table 5](#) below:

### 9.4.3 Safety Assessments

Safety evaluations include AEs, ophthalmic imaging and examinations, BCVA (ETDRS) score (assessed as both an efficacy and safety endpoint), vital signs, laboratory safety (biochemistry and haematology), [REDACTED]

AEs will be summarised in two parts: systemic events and ocular events. For systemic events, data will be displayed according to treatment received (low dose [REDACTED] vg, high dose [REDACTED] vg, and untreated). Ocular events will be displayed according to treatment allocation (including GT005 dose group) and study eye (study eye and contralateral eye).

All AEs (overall, by seriousness, by severity, by relationship) recorded throughout the study will be reported following classification according to the Medical Dictionary for Regulatory Activities (MedDRA) dictionary. [REDACTED]

Systemic safety evaluations including vital signs, laboratory safety, [REDACTED] will be summarised over time by dose and overall.

Ocular safety evaluations including ophthalmic examination variables (cataract grading, intra-ocular pressure, etc.) and BCVA scores will be summarised in the same manner as ocular efficacy variables, dependant on data type.

[REDACTED]  
[REDACTED]  
[REDACTED]  
[REDACTED]  
[REDACTED].

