### Safety Assessments

Safety evaluations include AEs, ophthalmic imaging and examinations, BCVA and Low Luminance Visual Acuity for LLD (ETDRS) score (assessed as both an efficacy and safety endpoint), vital signs, laboratory safety (biochemistry and haematology), and

[REDACTED]

AEs will be summarised in two parts: systemic events and ocular events. For systemic events, data will be displayed according to treatment received (untreated, low dose [REDACTED] vg) and high dose [REDACTED] vg]). Ocular events will be displayed according to treatment allocation (including GT005 dose group and untreated control) and study eye (study eye and contralateral eye).

All AEs (overall, by seriousness, by severity, by relationship), including adverse events of special interest, recorded throughout the investigation will be reported following classification according to the Medical Dictionary for Regulatory Activities dictionary.

Systemic safety evaluations including vital signs, laboratory safety [REDACTED] will be summarised over time by dose and overall.

Ocular safety evaluations including ophthalmic examination variables (cataract grading, intra-ocular pressure, etc.) and BCVA scores, will be summarised in the same manner as ocular efficacy variables, dependant on data type.

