### 8.4 Classification of an Adverse Event

#### 8.4.1 Severity Assessment

AEs will be classified as mild, moderate or severe according to the following criteria:

Mild: Does not interfere with subject's usual function.

Moderate: Interferes to some extent with subject's usual function.

Severe: Interferes significantly with subject's usual function.

AE severity will be assessed at the site by the Investigator or a medically qualified designee.

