### **2.7.1 Adverse events (AEs)**

Only AEs that occurred during the study period (from the date of randomization to the end of study) will be summarized. AEs recorded after screening but before the date of randomization will be listed only.

**Treatment-emergent Adverse Event (TEAE):** An adverse event is considered treatment emergent if the start date/time of the event is on or after the date of randomization, irrespective of the treatment arm. The primary summaries of AEs will be based on TEAEs.

The number (and percentage) of subjects with AEs will be summarized separately for ocular (study eye and fellow eye) and non-ocular events by treatment group in the following ways unless otherwise specified:

- Overall summary of death, subjects with any AE, any severe AE, any study treatment-related AE, any surgical procedure related AE, any AE leading to study discontinuation, any serious AE (SAE), any study treatment-related SAE, any surgical procedure related SAE, any SAE leading to study discontinuation
- AEs by primary SOC and PT
- AEs related to study treatment by SOC and PT (separately for study eye and non-ocular)
- AEs related to surgical procedure by SOC and PT (separately for study eye and non-ocular)
- SAEs by primary SOC and PT

- SAEs related to study treatment by SOC and PT (separately for study eye and non-ocular)
- SAEs related to surgical procedure by SOC and PT (separately for study eye and non-ocular)

A subject with multiple adverse events within a primary SOC is only counted once towards the total of the primary SOC.

All AEs, deaths, and SAEs (including those from the pre- and post-treatment periods) will be listed and those collected after the use of alternative GA therapies/medications, or during the pre-treatment, post-study period will be flagged. In addition, subjects who are not receiving treatment due to surgical procedure-related AEs will be listed separately by treatment group.

The MedDRA version used for reporting the AEs will be described in footnote.

For the legal requirements of ClinicalTrials.gov and EudraCT, two required tables on “on-treatment/treatment emergent” adverse events which are not serious adverse events with an incidence greater than 2% (or other cutting point as appropriate) and on “on-treatment/treatment emergent” serious adverse events and SAE suspected to be related to study treatment will be provided by system organ class and preferred term on the safety set population (i.e., the FAS of this study).

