### **2.7.1.1 Adverse events of special interest / grouping of AEs**

An AESI (serious or non-serious) is one of scientific and medical concern specific to the Sponsor's product or program, for which ongoing monitoring and rapid communication by the Investigator to the Sponsor can be appropriate. AESIs should also be assessed as to whether it fits the criteria of an SAE and reported appropriately. AESI should be reported as per reporting requirements [Protocol Section 8.3].

The number and percentage of subjects with AESIs will be summarized separated for ocular (study eye and fellow eye) events by category, PT, and treatment groups. In addition, AESIs related to the study treatment and/or surgical procedure will be summarized by category, PT and treatment groups.

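### The protocol commits to reporting adverse events by severity, but the SAP tabulates only an any-severe row and its list of changes does not say so

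*Protocol*

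**What the plan says.** **Protocol.** Section 9.4.3 states that "All AEs (overall, by seriousness, by severity, by relationship) recorded throughout the study will be reported following classification" by MedDRA. The synopsis, under Safety Assessments, has the parallel sentence: "All AEs (overall, by seriousness, by severity, by relationship), including adverse events of special interest, recorded throughout the investigation will be reported". Section 8.4.1 sets the scale: "AEs will be classified as mild, moderate or severe according to the following criteria".

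**SAP.** Section 2.7.1 says that AE counts and percentages will be "summarized separately for ocular (study eye and fellow eye) and non-ocular events by treatment group". It opens its list of outputs with "Overall summary of death, subjects with any AE, any severe AE, any study treatment-related AE, any surgical procedure related AE" and continues with discontinuations and the SAE equivalents. The SOC/PT tables that follow cover all AEs, SAEs, and AEs and SAEs related to treatment or to the surgical procedure. Section 2.7.1.1 summarises AESIs for study-eye and fellow-eye "events by category, PT, and treatment groups". Section 5.2 defines mild, moderate and severe as the scale for the study. Section 4 lists the departures from the protocol's analyses.

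**The concern.** The protocol places severity alongside seriousness and relationship. The SAP carries the other two through to tables by event term and reduces severity to one row. A team that programs exactly what SAP 2.7.1 lists will not produce an AE summary by severity, and a reader of Section 4 would not learn that a protocol commitment had been cut back.

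Safety and tolerability is a secondary objective, with the frequency of treatment-emergent AEs (TEAEs) as its endpoint. GT005 is a gene therapy given once by surgery, and the protocol notes that treatment cannot be withdrawn once surgery has taken place. Grade by event term is therefore a reasonable thing for a reader of the study report to expect. Suppose a term occurs in the same share of two dose groups, all mild in one and all moderate in the other. The planned tables would show the same percentage for that term and would add nothing to either any-severe row.

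**Working it through.** The point is a comparison of texts. There is no sample size, power or event figure to reproduce.

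**Step 1: the protocol's breakdowns against the SAP's tables**

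| Protocol breakdown (9.4.3, synopsis) | SOC/PT table in SAP 2.7.1 | Row in the overall summary |
|---|---|---|
| Overall | Yes, all AEs | Any AE |
| Seriousness | Yes, SAEs | Any SAE |
| Relationship | Yes, to treatment and to procedure, each for AEs and for SAEs | Related AEs and related SAEs, for treatment and for procedure |
| Severity | None | Any severe AE only |

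Beyond overall, three breakdowns are promised. Two have SOC/PT tables and one has none.

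The other outputs in 2.7 do not fill the gap. The registry tables in 2.7.1 are by SOC and PT without grade, the rule for merging consecutive events disregards severity, and the deaths table is by SOC and PT.

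**Step 2: what the single row can show**

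The row appears for three treatment groups (SAP 2.1.1.1) and three locations: 3 × 3 = 9 cells. Severe events can therefore be compared across dose groups, but not by term. If every event is graded, subjects with any AE minus subjects with any severe AE gives those whose worst grade is mild or moderate. Nothing planned splits that remainder. Of three grades collected, one is displayed.

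**Step 3: AESIs**

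The protocol synopsis puts AESIs inside the by-severity commitment. SAP 2.7.1.1 classifies them by category, PT, treatment group and relationship, and does not use severity.

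**Step 4: listings**

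SAP 2.7.1 lists all AEs, and 2.7 says that listings are by treatment group. The AE listing's columns are not specified beyond certain flags. By contrast, the SAP does name the main columns of the medical history listing (2.3.3) and the medication listings (2.4.2). Severity may appear in the AE listing, but the SAP neither requires nor excludes it.

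**Step 5: the record of changes**

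SAP Section 4 has five items: the Week 48 interim analysis removed, the safety set removed, the estimand simplified, the primary analysis changed to MMRM, and no subgroup of interest. Items on AE severity: 0.

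**Step 6: the definition behind the row**

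Protocol 8.4.1 calls an event severe if it interferes significantly with usual function. SAP 5.2 requires that it prevent normal activities. An event that interferes significantly without preventing activity is severe under the first and falls short of severe under the second. The only severity figure planned depends on this boundary.

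**The case against.** **The protocol does not prescribe a layout.** It says that AEs will be reported by severity. It does not ask for SOC by PT by maximum grade, and blacked-out text follows the sentence in 9.4.3. On this reading a severe row plus listings is partial delivery. That is fair as to format. However, the visible sentence treats severity on a par with two breakdowns that the SAP does tabulate by term, and a severe row alone does not report mild and moderate events by severity.

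**Other outputs capture the important harms.** SAEs have SOC/PT tables, AESIs have category tables, and losses of at least 15 and at least 30 letters of BCVA are tabulated for each eye. This stands, and it limits the consequence. None of these outputs is graded severity by event term.

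**The study is exploratory, ending early and small at the high dose.** With about 10 high-dose subjects, a listing can be read directly and proportions are imprecise: an assumed 4 of 10 has an exact 95% interval of about 12% to 74%. This too stands, and the tables would be descriptive only. But about 202 subjects were planned overall, and a listing does not summarise a pattern across groups. SAP 2.6.2 makes its outputs subject to data availability because of the termination. Grades are collected for every AE, so that caveat does not explain leaving severity out.

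**Stronger readings that the documents do not support.** A reader might infer that mild and moderate events cannot be told apart at all by event or dose. That goes too far: all AEs are listed by treatment group, the three-grade scale is retained, and the severe row is split by arm and location. A reader might also infer that the expected ocular harms differ between doses mainly in grade rather than in occurrence. No visible text says so; the risk section describes these harms largely by whether and how often they occur.

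**Conclusion.** The mismatch holds as a gap in the planned summary tables and in the record of changes. One of three promised breakdowns lacks any table by term, two of three grades are not shown separately in any table, AESIs have no severity summary, and Section 4 is silent. It should be corrected because following the SAP as written leaves a protocol-committed safety summary undelivered. It does not touch the primary analysis, and it does not mean that the grades are lost.

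The conclusion rests on the visible text. It assumes that no blacked-out passage elsewhere adds a severity table; the SAP's table of contents shows no hidden heading within 2.7. It does not depend on arm sizes or event rates.

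**What to change.** 1. In SAP 2.7.1, add TEAEs by primary SOC, PT and maximum severity (mild, moderate, severe) by treatment group, separately for study eye, fellow eye and non-ocular events. Count each subject once per term at the worst grade, and state how an ungraded event is shown.
2. In SAP 2.7.1.1, add maximum severity to the AESI table.
3. Name severity as a column of the AE listing.
4. Reconcile the severity definitions in protocol 8.4.1 and SAP 5.2, and state which wording the recorded grades follow.

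If the sponsor prefers not to add the tables, the reduction should at least be recorded and justified in Section 4.

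**Cost:** a SAP update and about five extra descriptive tables (three for TEAEs by location, two for AESIs by eye), from grades already collected. No new data are needed. The SAP's document history places this version before final database lock, so the change can be made in the same document if lock has not yet occurred.

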#### **1.6.1.2 Risks Associated with the Surgical Procedure and Study Procedures**

The surgical technique employed for this clinical study has been developed for and successfully used for the choroideremia subretinal gene therapy clinical studies [MacLaren 2014; Xue 2017]. Risk mitigation strategies have also been developed to minimise foveal or retinal stretch during vector delivery, or prevent post-surgical ocular inflammation. A careful pre-operative assessment of the retina is done as part of surgical planning, with a range of visual function tests as well as retinal imaging to determine the functional and structural integrity of the targeted retina. The risks include:

**Intraocular inflammation** [REDACTED] A transient visual loss may be observed in the first days post-surgery due to the bleb related foveal detachment. This can be minimised by avoiding injecting into areas of retinal thinning and by not detaching the fovea, if it is deemed not necessary. Retinal detachment usually regresses over 24 hours when the subretinal fluid resolves and retinotomy self-seals. Structural recovery of the retina following iatrogenic detachment of the macula generally occurs within 1 month [Xue 2017]. Persistent retinal detachment, due to persistence of the vector bleb, can occur in less than 1 in 100 cases and may be effectively managed by retinopexy with or without appropriate intraocular tamponade. An ocular examination of the eye treated with GT005 will be performed by the Vitreoretinal Surgeon or designee on post-surgical Day 2, at Week 1 (Day 8) and Weeks 5, 12, 24, 36, 48, 72, and 96 to ensure adequate monitoring. Subjects will also be contacted by telephone per the schedule of assessments for the review of adverse events (AEs).

**Cataract formation** is associated with any vitrectomy procedure and is also a risk of periocular or topical steroid use. In a published study from [Feng 2014], cataract appeared in approximately 40% of subjects following pars plana vitrectomy and resulted in a cataract extraction over the following 2 years. In publicly available safety data, voretigene neparvovec

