(Luxturna®), a subretinally delivered AAV2-RPE65 for the treatment of RPE65 retinal dystrophy, was administered in 81 eyes and of those, 11 eyes (14%) from seven subjects had documented progression of existing cataract or formation of new cataract. Three subjects had their cataract successfully extracted and other cataract cases did not receive elective extraction procedures [[Voretigene Neparvovec FDA ACM 2017](#)]. The study population of advanced AMD subjects is expected to have a mean age above or equal to 60 years and therefore may have already undergone a cataract extraction. At screening, subjects participating in this GT005 study and assessed as likely to require cataract surgery during the 12-month study period will not be included or will be offered the option of removing their cataract before being (re)screened in the study. Participants who develop cataracts during the study may undergo cataract surgery if deemed clinically necessary; if surgery is performed, it should be carried out at least 4 weeks before Week 48 visit.

**Intraocular pressure elevation** is a risk associated with vitrectomy procedures [[Chang 2006](#)] and periocular or topical steroids [[Kersey 2006](#)]. In publicly available safety data, voretigene neparvovec (Luxturna®), had reports of elevation in intraocular pressure in 8 of 81 eyes treated (10%). Subjects will have intraocular pressure (IOP) checked at every visit to ensure adequate monitoring and therapies prescribed as needed based on local standard. At screening, subjects with moderate or advanced glaucoma will not be included in the study to minimise this risk.

**Worsening of vision** is an uncommon risk associated with the surgical procedure or vitreous tap and could be the result of endophthalmitis or retinal damage. Risk is mitigated by design of the surgical procedure, Surgeon qualification standards, and close monitoring post-operatively.

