### 8.3 Adverse Events of Special Interest

An AESI (serious or non-serious) is one of scientific and medical concern specific to the Sponsor's product or program, for which ongoing monitoring and rapid communication by the Investigator to the Sponsor can be appropriate. AESIs should also be assessed as to whether it fits the criteria of an SAE and reported appropriately.

It is anticipated that there may be transient decreases to visual acuity related to the subretinal injection surgical procedure. A transient visual loss may be observed in the first days post-surgery due to bleb-related foveal detachment, if performed. Transient surgery-related events of decreases in visual acuity are defined as decreases occurring in close temporal association (within 24 hours) with the surgical administration of the study medication, and which are resolving at Week 1 (Visit 3) post-surgery.

Additionally, there is a known risk of cataract associated with any vitrectomy procedure. A published review from [Feng 2014] shows cataract to be common following pars plana vitrectomy with about 40% of patients requiring a cataract extraction over the following 2 years.

Transient, surgically-related decreases in visual acuity, as well as cataract will not be classified as AESI.

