### 2.7.4 Laboratory data

Laboratory parameters listed in [Table 2-1](#) will be presented graphically using boxplots of absolute change from baseline values by treatment group and visit. No summary by visit tables will be provided.

A summary table with number and percentage of subjects satisfying the criteria representing clinically relevant abnormalities defined in [Table 2-1](#) at any visit will be presented. A listing of subjects satisfying at least one criterion in [Table 2-1](#) at any visit will also be presented.

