### 2.7.5.2 Vital signs

A listing of subjects satisfying at least one criterion in [Table 2-2](#) at any visit will be presented.

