## 4 Change to protocol specified analyses

The Week 48 interim analysis was removed.

The Safety Analysis Set (SAF) was removed.

The estimand framework was simplified. Analysis for the primary endpoint was changed to MMRM.

Subgroup of interest is not applicable.

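### The protocol promises summaries of intraocular pressure and cataract grading, but the readable SAP plans none and its list of changes does not say so

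*Protocol*

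**What the plan says.** **Protocol.** Section 9.4.3 commits to this: "Ocular safety evaluations including ophthalmic examination variables (cataract grading, intra-ocular pressure, etc.) and BCVA scores will be summarised in the same manner" as the ocular efficacy variables, depending on data type. The synopsis repeats the commitment. Section 9.4.3 also says that vital signs and laboratory safety will be summarised over time, by dose and overall.

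Section 1.6.1.2 lists cataract and raised IOP among the risks of the procedure. Of cataract it says that it "is associated with any vitrectomy procedure and is also a risk of periocular or topical steroid use". Section 7.3.1 requires IOP and AREDS lens grading as part of the examination of both eyes. Section 8.3 adds: "Transient, surgically-related decreases in visual acuity, as well as cataract will not be classified as AESI".

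**SAP.** Readable section 2.7 covers AEs, AEs of special interest (AESIs), deaths, loss of BCVA, laboratory data, ECG (not applicable) and vital signs. For laboratory data, 2.7.4 says: "No summary by visit tables will be provided". For vital signs, the output in 2.7.5.2 is "A listing of subjects satisfying at least one criterion in" Table 2-2. Section 4 lists changes from the protocol: the Week 48 interim analysis, the safety set, the estimand and primary model, and the subgroup.

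**The concern.** The SAP says in its introduction that it describes analyses planned in, or changed from, the protocol. A protocol commitment should therefore appear either as a planned output or as a recorded change. For IOP and cataract grading it appears as neither.

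Safety and tolerability is a secondary objective, and these are two complications that the protocol itself expects from vitrectomy and steroid use. An AE table captures an event once an investigator judges it worth reporting. Scheduled IOP readings and lens grades do not pass through that judgement, and they show shifts too small to be called an event. They also give the fellow eye as a comparison. Development has stopped and treated subjects are moving to long-term safety follow-up, so the safety description is one of the more lasting results of the study.

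**Working it through.** There is no sample size or power figure to reproduce. The check sets the texts side by side and counts a few items.

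**1. Commitment against plan**

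| Item | Protocol 9.4.3 | Readable SAP | In SAP section 4? |
|---|---|---|---|
| BCVA | As ocular efficacy variables | 2.6.2 item 4.a (repeated-measures model by visit); 2.7.3 (losses of at least 15 and 30 letters, both eyes) | Not needed |
| IOP | As ocular efficacy variables | Nothing | No |
| Cataract grading | As ocular efficacy variables | Nothing | No |
| Vital signs | Over time, by dose and overall | 2.7.5.2: listing of subjects with a notable value | No |
| Laboratory | Over time, by dose and overall | 2.7.4: boxplots of change by group and visit, an abnormality table and a listing, for the Table 2-1 tests | No |

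The BCVA part of the sentence reached the SAP; the ophthalmic examination part did not. The baseline ocular list in SAP 2.3.2 also has no IOP or lens status. Section 4 does record safety changes ("The Safety Analysis Set (SAF) was removed"), so silence there does not mean that safety was outside its scope.

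For laboratory data, Protocol Table 4 has 25 biochemistry and 13 haematology parameters, 25 + 13 = 38. SAP Table 2-1 has 12.

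**2. Could a general clause cover the omission?** The clauses allowing outputs as data availability permits are in SAP 2.5.2 and 2.6.2, not in 2.7. SAP 2.1.1.4 says that data from unscheduled visits will be listed. That might bring in a stray IOP reading, but not the scheduled ones.

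**3. Could blacked-out text hold the analysis?** In the SAP contents, 2.7.5, 2.8, 2.9 and 2.10 all start on page 21. The blanked entries, on pages 23 and 24, follow 2.10 and so lie outside the safety section. The abbreviation list keeps TAb and RPE, which the readable text does not use, but has no IOP or AREDS. A hidden analysis is unlikely, though it cannot be excluded.

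**4. What is collected.** By the visit sections of Protocol 6.1, ophthalmic examinations after baseline are:
- GT005: Day 2 and Weeks 1, 5, 8, 12, 24, 36, 48, 72 and 96, which is 10.
- Control: Weeks 12, 24, 36, 48, 72 and 96, which is 6.

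The difference, 10 − 6 = 4, is the four early visits that only GT005 subjects have. A fair comparison therefore uses the six common visits.

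**5. Background rates in Protocol 1.6.1.2.** For another subretinal AAV2 product, IOP rose in 8/81 = 9.9% of eyes (printed as 10%), and cataract formed or progressed in 11/81 = 13.6% (printed as 14%). These are not estimates for GT005. They show only that the protocol does not treat the risks as negligible.

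**6. Other routes to the same information.** SAP 2.4.2 summarises concurrent procedures by treatment group, with study eye and fellow eye distinguished, so a cataract extraction could appear there. It also lists concomitant medications with indication and laterality, so IOP-lowering drugs could appear. SAP 2.7.3 tabulates BCVA loss. None of these reports IOP or lens grade.

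**The case against.** The strongest reply is that this is a reduced SAP for a programme stopped after a futility analysis. The endpoint for the safety objective is the frequency of treatment-emergent AEs, and that is fully tabulated. The AE definition in Protocol 8.1 includes abnormal results of an investigation, so a marked rise in IOP or a clear lens change should be reported anyway. AESIs are tabulated by category in SAP 2.7.1.1, and since the readable text does not list the categories, raised IOP may be one of them.

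Much of this stands. The gap is in descriptive reporting and leaves the safety endpoint itself untouched. But an AESI table is still an AE table, and cataract is expressly kept out of it. A decision to cut outputs is legitimate; section 4 is the place to record it.

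A reader might also infer more than the documents support:

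- *That AEs are the sole source.* They are not, given the outputs in step 6 of the working.
- *That the missing tables would correct for unmasked reporting.* Site staff know GT005 from control (Protocol 3.4.1; in Part 1 they are masked to dose), and they take the IOP readings and grade the lens.
- *That the unused readings can be counted as planned subjects times visits.* The study is ending early, so that product is a ceiling and not an estimate.
- *That the cataract rate is diluted by a known factor because some eyes have no natural lens at entry.* Protocol 1.6.1.2 says only that subjects may already have had an extraction. The documents give no proportion. They also do not show which eyes form the denominator of the published cataract extraction rate that the protocol cites.

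**Conclusion.** The point holds as an undocumented departure from the protocol. Two ocular safety variables named in both the synopsis and 9.4.3 have no specified output in the readable SAP and no entry in section 4. Vital-signs and laboratory summaries are cut back with the same silence, although the laboratory boxplots keep a by-visit view for 12 of the 38 parameters.

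The consequence is that cataract and raised IOP would be judged essentially from AE reports, helped by indirect signals. The data remain in the database, so nothing is beyond recovery. No numerical bias can be attached to the omission, and none is claimed. The conclusion rests on the readable text and on the reasonable but unprovable assumption that the blacked-out SAP sections do not contain these analyses. It should be put right, but it does not touch the primary analysis.

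**What to change.** Add a subsection to SAP 2.7.5, by treatment group and visit, separately for study eye and fellow eye:

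1. IOP: observed value and change from baseline, in the descriptive format that SAP 2.6.2 already uses for low luminance difference.
2. AREDS nuclear, cortical and posterior subcapsular grade: number and percentage in each grade, or shift from baseline.
3. Arms compared at the common visits, Weeks 12 to 96, with the GT005-only visits shown separately. Outputs as data availability allows, since follow-up is being cut short.
4. A sentence stating that these are site measurements made with knowledge of GT005 or control allocation.

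In SAP section 4, record that vital signs are reduced to a listing of notable values, and laboratory data to boxplots plus an abnormality table and listing. If the sponsor prefers not to produce the IOP and lens tables, section 4 should say so and give the reason.

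The cost is SAP wording and a few standard descriptive tables on data the protocol already requires. The SAP was finalised before the final database lock, so this is best settled before that lock.
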